5.3.1.2.4. Sensitivity Analysis

A simple semi-parametric Bayesian normal dynamic linear model (NDLM) will also be explored for does response to complement the frequentist gMCP-Mod analysis as a sensitivity analysis. This analysis will be performed through FACTS engine which will only be for internal use and will not be presented in Clinical Study Report (CSR).

A Bayesian approach will be used for this analysis. The longitudinal beta-binomial model will be used to analyze the primary endpoint PASI 75 at Week 16 in conjunction with participant's primary endpoint values.

$$Y_{di} \sim \text{Bernoulli}(P_d)$$

where Y_{di} is the PASI 75 outcome measures at 16 weeks for the i^{th} participant in arm d respectively. P_d is the underlying response rate for arm d . The response rates were transformed onto the log-odds scale to allow modeling on a continuous scale:

$$\theta_d = \log\left(\frac{P_d}{1 - P_d}\right).$$

The logit response rate is modeled through simple normal dynamic linear model (NDLM) for active dose groups while placebo group is modeled separately with the following non-informative priors derived from previous psoriasis studies:

$$\theta_d \sim N(-2.75, 10)$$

Similar to the primary analysis, the sensitivity analysis will include data from all randomized participants who received at least one administration of study intervention (FAS, Section 4.1) based on their assigned intervention group, regardless of the actual intervention received.

Participants with ICEs 1-2 before Week 16 will be considered as PASI75 non-responders at Week 16. Participants with ICE 3, observed PASI data after this ICE will be utilized in the analysis. For participants experiencing multiple ICEs, an ICE 2 will override an ICE 3.

After accounting for the ICEs for the primary estimand, the remaining missing data of the primary endpoint at Week 16 will remain missing, and no imputation will be performed outside of the FACTS Engine. However, missing data will be imputed inside FACTS Engine by multiple imputation when performing the model-based analysis using Bayesian longitudinal model.

5.3.1.2.5. Analysis for Supplementary Estimands

The analyses specified below for supplementary estimands will be applied to the pairwise comparisons for the primary endpoint.

5.3.1.2.5.1. Supplementary Analysis 1 (Hypothetical Estimand)

Under this estimand, PASI 75 response will be considered missing after intercurrent events; and after accounting for the ICEs, all other missing data will be remaining missing. All missing data will then be imputed using multiple imputations (MI) by fully conditional specification (FCS).

More specifically, the missing PASI75 responses will be imputed with FCS logistic regression including treatment group, baseline PASI score, and PASI75 response status through Week 16 in the model with seed = 789 and 500 imputations. The proportion difference of PASI75 response between each JNJ-77242113 group and placebo group at Week 16 adjusted for baseline weight category (≤ 90 kg, > 90 kg) using Mantel-Haenszel weight and its 95% CI combining multiple datasets will also be provided. A CMH test stratified by baseline weight category (≤ 90 kg, > 90 kg) will be used to obtain the CMH statistic for each imputed dataset.

The values of the general association test statistics from the CMH test for each imputed dataset will be transformed using the Wilson-Hilferty transformation to create a more normal distributed statistic:

$$Z = \frac{(CMH)^{(1/3)} - 7/9}{(2/9)^{(1/2)}}$$

The resulting transformed values will be combined using SAS PROC MIANALYZE and obtain the overall p-value for the CMH test. Difference in PASI75 response rates at Week 16 between each of the active intervention groups and the placebo group at Week 16 adjusted for baseline weight category using Mantel-Haenszel weight and its 95% CI combining multiple datasets will also be provided.

5.3.1.2.5.2. Supplementary Analysis 2 (Treatment Policy Estimand)

The primary endpoint will also be analyzed utilizing the treatment policy estimand. For participants who experience an intercurrent event through Week 16, the analysis will be performed using observed data regardless of intercurrent events. Missing data will be imputed using multiple imputation method specified in Section [5.3.1.2.5.1](#).

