6.3. Measures to Minimize Bias: Randomization and Blinding

Intervention Allocation

Procedures for Randomization and Stratification

Dynamic central randomization will be implemented in conducting this study. Participants will be assigned to 1 of 6 intervention groups based on an algorithm implemented in the interactive web response system (IWRS) before the study. Dynamic central randomization minimizes the imbalance in the distribution of the number of participants across intervention groups within the levels of each individual stratification factor: study site and baseline weight (≤ 90 kg, > 90 kg). In addition, the Japanese sites will be pooled in the randomization process to better ensure treatment balance across Japanese participants. Based on the algorithm, the IWRS will assign a unique intervention code, which will dictate the intervention assignment and matching study intervention kit for the participant.

Blinding

The investigator will not be provided with randomization codes. The codes will be maintained within the interactive web response system (IWRS), which has the functionality to allow the investigator to break the blind for an individual participant.

Data that may potentially unblind the intervention assignment (ie, study intervention plasma concentrations, anti-JNJ-77242113 antibodies, study intervention preparation/accountability data, intervention allocation, and biomarker data) will be handled with special care to ensure that the integrity of the blind is maintained and the potential for bias is minimized. This can include making special provisions, such as segregating the data in question from view by the investigators, clinical team, or others as appropriate until the time of database lock and unblinding.

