5.3.1.2.3. Analysis Methods for the Primary Estimand

The primary endpoint will be analyzed based on the primary estimand (Section 5.3.1.2.1) and the data from all participants in FAS (Section 4.1) will include data from all randomized participants who received at least one administration of study intervention based on their assigned intervention group, regardless of the actual intervention received.

Participants with ICEs 1-2 before Week 16 will be considered as PASI75 non-responders at Week 16. Participants with ICE 3, observed PASI data after this ICE will be utilized in the analysis. After accounting for the ICEs for the primary estimand, participants with the missing data of the primary endpoint at Week 16 will be considered as non-responders.

The MCP-Mod will be used to test if there is a positive overall treatment effect based on candidate dose-response models. For each candidate model a contrast test statistic, based on a linear combination of the treatment estimates per dose will be derived. The contrast coefficients will be chosen to maximize the power to detect the pre-specified candidate models. The global test decision is based on the maximum of the contrast test statistics. The overall positive dose-response will be tested at a 2-sided 5% significance level. This procedure takes into account the multiplicity arising from testing several models and thus preserving the family wise Type I error rate.

CCI

Generalized Multiple Comparison Modelling (gMCP-Mod)

To demonstrate the dose-response relationship across JNJ-77242113 treatment groups and placebo for the primary endpoint, the primary analysis will be based on a generalized Multiple Comparisons and Modeling (gMCP-Mod) analysis^{1,2}. This analysis tests for a dose-response relationship, allowing for uncertainty in the dose-response relationship through inclusion of contrasts from multiple pre-specified candidate models to assess dose-response. If a dose-response relationship exists, then fitted estimates for the incidence of the primary endpoint will be calculated in each of the treatment groups using the selected dose-response models.

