5.4.1.3.1. Binary Endpoints

The binary secondary endpoints at Week 16 will be analyzed using the estimands described in section 5.4.1.2.2. The analysis strategy for ICEs and missing data will be handled in the same manner as the primary estimand for the primary analysis (Section 5.3.1.2.3). The proportions of participants for the above secondary efficacy endpoints will be summarized for each intervention group.

The Cochran-Mantel-Haenszel chi-square statistic stratified by baseline weight category (≤ 90 kg, > 90 kg) at a 2-sided significance level of 0.05 will be used. Difference in response rates between

each of the active and placebo groups at Week 16 adjusted for baseline weight category (≤ 90 kg, > 90 kg) using Mantel-Haenszel weight and the corresponding 95% CI will be presented.

In case of rare events, the Fisher's Exact test will be used for treatment comparisons in binary response endpoints. The proportion differences between JNJ-77242113 groups and placebo and the exact confidence intervals will be provided.

5.4.1.3.1.1. Analysis for Supplementary Estimands

Similar to the primary analysis of pair comparison, the analyses specified in Section 5.3.1.2.5.1 (Hypothetical Estimand) and Section 5.3.1.2.5.2 (Treatment Policy Estimand) for supplementary estimands will be applied to the following secondary endpoints:

- Proportion of participants achieving PASI 90 ($\geq 90\%$ improvement from baseline in PASI) at Week 16
- Proportion of participants achieving PASI 100 (100% improvement from baseline in PASI) at Week 16
- Proportion of participants achieving an IGA score of cleared (0) or minimal (1) at Week 16
- Proportion of participants achieving an IGA score of cleared (0) at Week 16

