5.5.1.2.3. Analyses Related to PASI

- The change from baseline in PASI total score will be summarized by treatment group over time through Week 16.
- The proportions of PASI 75 responders, PASI 90 responders, and PASI 100 responders; the proportions of PASI 75 responders, PASI 90 responders, and PASI 100 responders by weight (≤ 90 kg, > 90 kg) will be summarized by treatment group over time through Week 16.
- The proportions of participants achieving $\geq 75\%$ improvement, $\geq 90\%$, or achieving 100% improvement from baseline in PASI disease component (Induration, Erythema, and Scaling) and region component (head, trunk, upper extremities, and lower extremities) will also be summarized at Week 16.

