5.7. Other Analyses

5.7.1. Pharmacokinetics

5.7.1.1. JNJ-77242113 Concentrations

The PK evaluable population is defined as all the participants who received at least 1 complete dose of JNJ-77242113 and had at least 1 valid blood sample drawn for PK analysis after their first dose of JNJ-77242113.

Plasma JNJ-77242113 concentrations will be summarized by visit and treatment group. Plasma, concentration will be summarized using descriptive statistics (i.e., n, arithmetic mean, standard deviation [SD], coefficient of variation [%CV], median, range [minimum and maximum], and interquartile [IQ] range) at each visit. PK data may be displayed graphically.

The following analyses will be performed as appropriate.

- Summary of plasma JNJ-77242113 concentration over time
- Proportion of participants with plasma JNJ-77242113 concentration below the lowest quantifiable concentration in a sample at each visit
- Summary of plasma JNJ-77242113 concentrations over time by baseline body weight (≤ 90 kg, > 90 kg). Other covariates may also be applied
- Plots of median plasma JNJ-77242113 concentrations over time
- Plots of median plasma JNJ-77242113 concentrations over time by baseline body weight (\leq median, $>$ median)

Concentrations below the lowest quantifiable concentration will be treated as zero in the summary statistics. All plasma concentrations below the lowest quantifiable concentration or missing data will be labeled as such in the concentration database. PK data may also be displayed graphically.

If feasible, population PK analysis of plasma concentration-time data of JNJ-77242113 may be performed using nonlinear mixed-effects modeling. Data may be combined with those of other selected studies to support a relevant structural model. Available baseline participant characteristics (eg, demographics, laboratory variables, genotypes, race) will be tested as potential covariates affecting PK parameters. Details will be given in a population PK analysis plan and the results of the population PK analysis will be presented in a separate report.

77242113PSO2001

For study 77242113PSO2001, PK analysis set (Section 4.1) will be used and the analyses will be summarized through Week 16.

For the analyses, a participants included in one and only one treatment group on the basis of the treatment regimen followed. The description of treatment groups is as follows:

- JNJ-77242113 25 mg QD
- JNJ-77242113 50 mg QD
- JNJ-77242113 25 mg BID
- JNJ-77242113 100 mg QD

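### The multiple-imputation model for the supplementary estimands omits baseline weight category, which stratifies the analyses run on the imputed data; adding it is a free, minor improvement

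*SAP*

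**What the plan says.** SAP 5.3.1.2.5.1 (hypothetical estimand) sets all PASI 75 data after an intercurrent event to missing and fills the gaps by fully conditional specification: "the missing PASI75 responses will be imputed with FCS logistic regression including treatment group, baseline PASI score, and PASI75 response status through Week 16". The seed and the number of imputations (500) are fixed in the same sentence. On each completed dataset, "A CMH test stratified by baseline weight category" is run, and Mantel-Haenszel differences adjusted for weight category are pooled.

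The method is then reused. For the treatment-policy estimand, SAP 5.3.1.2.5.2 says: "Missing data will be imputed using multiple imputation method specified in Section" 5.3.1.2.5.1. SAP 5.4.1.3.1.1 says that the analyses for "supplementary estimands will be applied to the following secondary endpoints", namely PASI 90, PASI 100, IGA 0/1 and IGA 0. No section adds weight to the imputation model.

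Elsewhere weight is treated as a design variable and possibly a prognostic one:
- Protocol 6.3 balances the arms "within the levels of each individual stratification factor: study site and baseline weight".
- The MMRM in SAP 5.4.1.3.2, also a missing-at-random analysis, includes weight category and its interaction with visit.
- SAP 5.5.1.2.3 plans "the proportions of PASI 75 responders, PASI 90 responders, and PASI 100 responders by weight".
- SAP 5.7.1.1 plans a "Summary of plasma JNJ-77242113 concentrations over time by baseline body weight".

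The primary estimand does not use this imputation. Under SAP 5.3.1.2.3, "participants with the missing data of the primary endpoint at Week 16 will be considered as non-responders".

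**The concern.** An imputation model should contain at least the variables used in the analysis of the imputed data. Here it does not. Imputed responses carry no weight effect beyond what baseline PASI and earlier PASI 75 status convey, so within an arm they are pulled toward the arm average whatever the participant's weight. The missing-at-random assumption is also made without conditioning on weight. If weight predicts both response and missingness, that assumption fails in a way that an observed covariate would largely repair.

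The imputation will be used. The hypothetical estimand discards everything after any of the three intercurrent events. Under the treatment-policy estimand, Week 16 gaps are foreseeable because Protocol 7.1 follows participants who stop treatment for only about four weeks after the last dose. At stake is the accuracy of analyses meant to show whether the pairwise results survive other ways of handling intercurrent events and missing data.

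**Working it through.** **The plan's own figure.** This point disputes no stated number. The nearest is the pairwise power in SAP 3.1: at least 90% for a 35-point difference with 40 per arm, two-sided 0.05, placebo 5% to 10%. With power = Φ{[d − 1.96·√(2·p̄(1−p̄)/n)] / √([p1(1−p1)+p0(1−p0)]/n)}, the result is 97.6% (5% vs 40%), 97.1% (6% vs 41%) and 95.4% (10% vs 45%). The claim is met, and adding an imputation covariate does not change it.

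**Scale.** With complete data at 6% vs 41%, the standard error of the difference is √[(0.06·0.94 + 0.41·0.59)/40] = 8.6 points. With missing data and imputation it came out between about 8 and 10, so about 9 is used below.

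**Inputs the documents do not give (assumed).** Share above 90 kg: 45% or 50%. Response by weight: for example 70% (≤90 kg) vs 50% (>90 kg) in a 60% arm. Missingness: from 5% to 30% by weight group.

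**Step 1: closed form.** Suppose missing responses are imputed at the observed arm rate. Let q be the share above 90 kg, pL and pH the response rates in the lighter and heavier groups, mL and mH their missing fractions, and m̄ the overall missing fraction. The bias in the arm's rate is

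q(1−q)(pL−pH)(mH−mL)/(1−m̄).

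- Equal missingness, mH = mL: bias 0.
- 70/50 response, 5%/20% missing, q = 0.5: 0.25·0.20·0.15/0.875 = +0.86 points.
- A placebo arm at 8/4 with the same missingness: 0.25·0.04·0.15/0.875 = +0.17 points, so the difference is biased by about +0.7.
- 45/30 response, 5%/15% missing, q = 0.45: 0.2475·0.15·0.10/0.905 = +0.41 points.
- If the lighter group is missing more (20%/5%), the 70/50 case becomes −0.86 points. The sign is not fixed.

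**Step 2: large-sample bias with earlier visits in the model.** Six arms: placebo 6%, active arms assumed at 35, 50, 55, 60 and 75%. Half of participants are above 90 kg. PASI 75 status at Weeks 4, 8 and 12 predicts Week 16, and the latent correlation between adjacent visits is 0.5 or 0.85. Bias in the overall active-minus-placebo difference, in points:

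| Response by weight (60% arm) | Missing ≤90 / >90 kg | Weight omitted | Weight included |
|---|---|---|---|
| 70/50 | 10% / 10% | 0 | 0 |
| 70/50 | 5% / 10% | +0.08 to +0.24 | −0.03 to +0.07 |
| 65/55 | 5% / 20% | +0.14 to +0.39 | −0.05 to +0.11 |
| 70/50 | 5% / 20% | +0.27 to +0.76 | −0.09 to +0.21 |
| 70/50 | 5% / 30% | +0.49 to +1.32 | −0.17 to +0.37 |

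**Step 3: small-sample simulation.** Six arms of 40, 45% above 90 kg, Week 12 and Week 16 responses, 15 imputations, 400 replicates per scenario, Mantel-Haenszel difference with Rubin's rules. The estimate without weight minus the estimate with weight was 0.1 point or less in size when missingness was unrelated to weight, and 0.4 to 0.9 points when the heavier group was missing more often. Empirical standard errors hardly moved (8.96 without vs 9.00 with; 9.53 vs 9.28; 7.97 vs 8.15). The Monte Carlo error of each bias estimate was 0.4 to 0.5 points. This run therefore shows the size of the shift and the lack of a precision cost; it cannot show which version lies closer to the truth. That rests on Steps 1 and 2.

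**The case against.** The strongest reply is that this hardly matters. The affected analyses are supplementary, pairwise and unadjusted for multiplicity; study success rests on gMCP-Mod. The bias needs two conditions that the documents do not supply: a weight effect on response, and missingness that differs by weight given arm, baseline PASI and earlier status. Planning summaries by weight does not show that weight matters; in SAP 5.7.5 it is one of many routine subgroups. All of this stands, and it sets the size of the point.

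It could also be said that the word introducing the predictor list leaves it open. That is weak in a passage that fixes the seed and the number of imputations.

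There is a fair question about sparse data. At 6% of 40, about 2.4 placebo responders are expected, and fewer for PASI 100 or IGA 0. The simulation used a small ridge penalty that the SAP does not specify, so it does not test convergence of the model as written. That risk already exists with treatment group in the model. One main effect probably adds little to it; a weight-by-treatment term would add more.

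Three stronger readings are tempting and are not supported:
- A reader might infer that the primary result is at risk. It is not: missing Week 16 data count as non-response there.
- A reader might infer that response rates reported within weight groups will be distorted. SAP 5.3.1.2.5.1 reports only the overall test and the overall adjusted difference. The by-weight PASI summaries (5.5.1.2.3) and the weight subgroup (5.7.5) call for no multiple imputation, and 5.5.1.2.1 carries the main estimand's missing-data handling to the exploratory Week 16 analyses.
- A reader might infer that the omission favours the drug. That holds only if the group that responds less is also missing more often.

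**Conclusion.** The omission is real, and the imputation model is narrower than the weight-stratified analysis that follows it. It contradicts nothing in the plan, and the plan is workable as written. The overall difference is essentially unbiased if missingness does not depend on weight. If weight predicts both response and missingness, the bias is roughly 0.3 to 0.9 points in either direction, up to about one tenth of a standard error of about 9 points. Weaker assumed inputs give less, and a 5%/30% missingness split gives up to about 1.3 points. All of these figures rest on assumed missing-data rates and weight effects. This is a minor point, worth acting on because the change costs almost nothing.

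**What to change.** In SAP 5.3.1.2.5.1, add baseline weight category (≤90 kg, >90 kg) to the FCS logistic model as a main effect. State that the same term applies in 5.3.1.2.5.2 and, for PASI 90, PASI 100, IGA 0/1 and IGA 0, in 5.4.1.3.1.1. Do not add a weight-by-treatment term, given the few placebo responders expected.

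The cost is one line of SAP text and one program term. Weight category is already collected as a randomisation factor. No new data or participants are needed, sample size, power and alpha are unchanged, and the simulation showed no meaningful loss of precision.

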5.3.1.2.6. Per Protocol Analysis

The primary efficacy endpoint will be evaluated for pairwise comparison in the PP population based on the primary estimand except that ICE 3 will not be applied. Participants with ICE 3 who do not complete all scheduled study administration prior to Week 16 will be excluded from the per protocol analysis. The same data handling rule and analysis method specified in Section 5.3.1.2.3 will be applied.

5.3.2. Study 77242113PSO2002

5.3.2.1. Definition of Primary Endpoint

The primary efficacy endpoint of 77242113PSO2002 study is the proportion of participants achieving PASI 75 at Week 36, defined as at least a 75% improvement in PASI from baseline of the originating study (77242113PSO2001). The definition of PASI responses is described in Section 5.3.1.1

5.3.2.2. Estimands

5.3.2.2.1. Primary Estimand

In this primary estimand, the components that are different from the definition of the primary estimand of study 77242113PSO2001 are the intervention attribute, Variable/endpoint, and Population level summary; and all other components are the same as the primary estimand as specified in Section 5.3.1.2.1.

Study intervention: JNJ-77242113 25 mg QD, 50 mg QD, 25 mg BID, 100 mg QD, 100 mg BID, and placebo → 100 mg QD

Variable/endpoint: Binary response variable, where a responder is defined as a participant achieving a PASI75 response at Week 36. A participant with an intercurrent event in categories 1-2 defined in Section 5.3.1.2.1 will be considered as a non-responder.

Population level summary: Descriptive summary statistics for the proportions of participants achieving a PASI 75 responses at Week 36 for each of the treatment groups.

Note: If the Week 0 visit for study 77242113PSO2002 takes place on a different day as the Week 16 visit of study 77242113PSO2001 with a gap greater than 4 weeks, the participants are allowed to take medications specified in 77242113PSO2002 that could improve psoriasis after 4 weeks from the Week 16 visit of study 77242113PSO2001 and before entering the study of 77242113PSO2002; ICE 2 specified in Section 5.3.1.2.1 will not be applied in this situation.

